9.3.1. Treatment-emergent Adverse Events

An AE will be regarded as treatment-emergent if it was present prior to receiving the first injection of rFVIIIFc and subsequently worsened in severity, or was not present prior to receiving the first injection but subsequently appeared before the patient's last visit on study or the follow-up phone call, whichever came later (or the date of withdrawal/loss to follow-up).

The algorithm for the determination of treatment emergence when an onset date is partially or completely missing is described below.

- If the onset time of an adverse event (if time is collected) is missing and the date of onset is the date of dosing, the AE is considered to be a TEAE.
- If the onset day of an adverse event is missing and the month and year of the onset of the AE are either the same or later than the month and year of the first treatment, the AE will be considered a TEAE.
- If the onset day of an adverse event is missing and the month and year of the onset of the AE precede the month and year of the first treatment, the AE will not be considered a TEAE.
- If the onset month of an adverse event is missing and the year of the onset of the AE is either the same as or later than the year of first treatment, then the AE will be considered a TEAE.
- If the onset month of an adverse event is missing and the year of AE onset precedes the year of first treatment, the AE will not be considered a TEAE.
- If the onset day, month, and year of an adverse event are missing, the AE will be considered to be a TEAE.
- If start date is partial but the stop date can be determined to be before the start of the first dose of study drug, then the AE will not be considered a TEAE.

9.3.2. Overall (Top-Line) Summary of Treatment-Emergent Adverse Events

A top-line summary of treatment-emergent adverse events (TEAEs) will be provided which tabulates the number and percentage of patients who experienced a TEAE, related TEAE, treatment-emergent SAE, or treatment-emergent related SAE; the number and percentage of patients who discontinued treatment and/or the study due to a TEAE; and the number and percentage of patients who died. This table will be presented by treatment regimen and for the inhibitor subgroups, as described in Sections 5.1.1.1 and 5.1.1.2 respectively.

This summary will also be presented by EPD entry compliance (see Section 6.6.2.3), <80% and $\geq 80\%$, where $\geq 80\%$ is considered compliant.

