#### **15.3.2. Serious Adverse Events**

Any SAE experienced by the subject between the time of signing the ICF and the Safety Follow-up Visit/Telephone Call is to be recorded on an SAE form, regardless of the severity of the event or its relationship to study treatment. SAEs must be reported to Quintiles Pharmacovigilance and the designated personnel within 24 hours as described in Section 15.3.3. Follow up information regarding an SAE must be reported within 24 hours.

Any SAE ongoing when the subject completes the study or discontinues from the study will be followed by the Investigator until the event has resolved, stabilized, or returned to baseline status.

In this study, the following events are considered medically important and must be reported as SAEs:

- A subject develops an inhibitor, as defined in Section 10.2.5.

CONFIDENTIAL

The information contained herein may not be used, disclosed, or published without the written consent of Bioerativ Therapeutics Inc.

- A subject develops a Grade 2 or greater allergic reaction in association with administration of rFVIII Fc defined as follows using the Recommendations for Grading of Acute and Subacute Toxic Effects on the WHO scale [[WHO Handbook 1979](#)]:
  - Grade 2: bronchospasm; no parenteral therapy needed
  - Grade 3: bronchospasm; parenteral therapy required
  - Grade 4: anaphylaxis
- A subject develops a vascular thrombotic event in association with the administration of rFVIII Fc, with the exception of IV injection site thrombophlebitis
- A subject undergoes major surgery

Allergic reactions, including anaphylaxis, have been reported with FVIII products. The subject's parents/caregivers (and the subject, if applicable) should be informed of early symptoms and signs of hypersensitivity reactions, including difficulty breathing, chest tightness, swelling of the face, rash, or hives. If such an event occurs while the subject is at home, the parents/caregivers should be instructed to seek immediate medical care for the subject.

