5.1.1.2. Inhibitor Subgroups

Selected tables will further be presented by the following groups:

- Patients in the inhibitor subgroup (see Section 5.1.2.5)
- Patients not in the inhibitor subgroup

For longitudinal data, the safety or efficacy periods included for these groups is the entire period, again as described in Section 5.4.

Patients in the inhibitor subgroup will be further split by the sub-classification of inhibitor as described in Section 5.1.2.5, namely:

- Patients with high-titer inhibitors
- Patients with low-titer inhibitors that meet the clinically meaningful criteria as defined in Section 5.1.2.5
- Patients with low-titer inhibitors that do not meet the clinically meaningful criteria

For this presentation, the analysis of longitudinal data will be presented for the entire safety or efficacy periods, dichotomized as described in Section 5.4.7, i.e.:

- From start of the relevant period up to the date of the positive inhibitor (all patients in the inhibitor subgroup combined)
- From date of positive inhibitor to the end of the relevant period

The definition of a positive inhibitor and the date of onset are described in Section 5.1.2.4.

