5.1.2.5. Subgroup Definitions

Surgery Subgroup

The Surgery Subgroup is defined as all patients who have undergone major surgery after first dose of study drug. This set will be described in the disposition table and all analyses and listings of major surgeries will be presented for this population.

Inhibitor Subgroup

Patients developing a positive inhibitor after exposure to rFVIII Fc will be included in Inhibitor Subgroup. Within this subgroup, there are several further classifications:

1. Patients with high-titer inhibitors, defined as in Section 5.1.2.4
2. Patients with low-titer inhibitors, defined as Section 5.1.2.4, that meet the below clinically meaningful criteria
3. Patients with low-titer inhibitors that do not meet the below clinically meaningful criteria

The delineation of clinically meaningful will be performed on a case-by-case basis via medical adjudication just prior to the interim or final analyses, based upon the data available for the analysis. This assessment will take account of relevant clinical factors, including but not limited to:

- Entry to the ITI sub-study
- Any bypassing or immunomodulatory agents received up to 4 weeks before inhibitor development and any time after
- Withdrawal from the study due to complications assessed as related to inhibitor development
- Any SAE of a bleeding event up to 4 weeks before inhibitor development or any time after

- A pattern of non-serious treated bleeding events which require a change in study drug (rFVIII Fc) regimen

Patients who undergo ITI will be part of the ITI Analysis Set (see Section 4.4). By definition, all high-titer inhibitors are clinically meaningful, as patients with high-titer inhibitors must either enter the ITI sub-study or withdraw.

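### In the top-line AE table by inhibitor subgroup, the any-TEAE and any-SAE rows for inhibitor patients will sit at or very near 100% because the event that defines the subgroup is itself a mandatory SAE; rows excluding that event should be added.

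*SAP*

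**What the plan says.** Protocol 15.3.2 introduces its list of special events with "In this study, the following events are considered medically important and must be reported as SAEs". The first item is "A subject develops an inhibitor, as defined in Section 10.2.5". SAP 9.3.7 carries medically important events over as SAEs (it cites Protocol 15.1.2, although the list is in 15.3.2).

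SAP 5.1.2.5 sets subgroup membership: "Patients developing a positive inhibitor after exposure to rFVIII Fc will be included in Inhibitor Subgroup". For the two columns with and without an inhibitor, SAP 5.1.1.2 states that "the safety or efficacy periods included for these groups is the entire period". A further presentation, by inhibitor sub-classification, splits follow-up into two windows: "From start of the relevant period up to the date of the positive inhibitor" (all inhibitor patients combined) and "From date of positive inhibitor to the end of the relevant period".

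The top-line table in SAP 9.3.2 tabulates "the number and percentage of patients who experienced a TEAE, related TEAE, treatment-emergent SAE, or treatment-emergent related SAE", together with discontinuations and deaths. On layout it says: "This table will be presented by treatment regimen and for the inhibitor subgroups, as described in Sections 5.1.1.1 and 5.1.1.2 respectively".

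SAP 9.3 leaves overdoses out of the AE tables unless they are judged to be AEs, and bleeds are not AEs unless serious. It states no exclusion for inhibitor events. SAP 9.3.10 plans no output for AEs of special interest. The list of tables in SAP 12 has one SAE table by system organ class and preferred term (SOC/PT), by treatment regimen.

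**The concern.** A subgroup defined by an event is compared with its complement on a row that counts the same event. The inhibitor column of the any-TEAE and any-SAE rows is then settled before any data arrive, and the contrast with inhibitor-free patients reflects how the subgroup was formed. It does not say whether inhibitor patients had more or fewer other serious events.

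This matters because safety is the primary objective. The top-line table is also the fullest AE summary in the plan: under SAP 9.3, AEs in major surgical or rehabilitation periods are counted there and in no other AE table. A reader who wants to know how inhibitor patients fared apart from the inhibitor would go to these rows first.

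**Working it through.** The plan gives no figure to reproduce: neither document states an AE or SAE rate for this table. The check is a chain of definitions, followed by an illustration on assumed values.

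**Chain of definitions**

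1. A patient is in the Inhibitor Subgroup if he has a confirmed positive inhibitor after exposure (SAP 5.1.2.5, 5.1.2.4).
2. That event must be reported as an SAE (Protocol 15.3.2, using the definition in 10.2.5).
3. It first appears after the first injection, so it is treatment-emergent (SAP 9.3.1).
4. It falls inside the column's window, which is the entire safety period (SAP 5.1.1.2).
5. Nothing removes it from the table (SAP 9.3, 9.3.2).

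For k inhibitor patients, both rows therefore print k/k = 100% when every inhibitor is reported as an SAE. The related-TEAE and related-SAE rows are not fixed in this way, because the investigator decides causality.

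**How far below k/k the rows could fall**

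The protocol's confirmatory sample is due about 2 to 4 weeks after the first; the SAP requires only at least 2 weeks. A patient confirmed later than about 4 weeks could enter the SAP subgroup without strictly meeting the protocol's SAE trigger. Sites may also under-report. If one patient is missed in this way and has no other SAE, the any-SAE row prints (k - 1)/k: 9/10 = 90%, 19/20 = 95%, 29/30 = 96.7%. The shortfall reflects timing or reporting, so the row is no more informative about other events.

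**Illustration (all inputs are assumptions)**

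Let k = 10, 20 or 30 inhibitor patients. Let r be the share of them with another SAE (20%, 40%, 60%), and q the share of inhibitor-free patients with an SAE (10%, 30%, 50%).

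- Planned row: 10/10, 20/20 or 30/30, that is 100% for every r.
- Row excluding the inhibitor event: 2, 4 or 6 of 10; 4, 8 or 12 of 20; 6, 12 or 18 of 30, that is 20%, 40% or 60%.
- Gap between the two rows: 100 - r = 80, 60 or 40 points.
- Difference from inhibitor-free patients: 100 - q in the planned row, r - q in the excluding row.

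| q | Planned row (any r) | Excluding, r = 20% | Excluding, r = 40% | Excluding, r = 60% |
|---|---|---|---|---|
| 10% | +90 | +10 | +30 | +50 |
| 30% | +70 | -10 | +10 | +30 |
| 50% | +50 | -30 | -10 | +10 |

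The planned difference does not move with r. In three of the nine cells it has the opposite sign to the difference for other SAEs.

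**Whether another planned output gives the count**

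- *Sub-classification table.* The pre-inhibitor column stays informative, for that part of follow-up only. The post-inhibitor columns open on the date of the first positive sample (SAP 5.1.2.4, 5.4.7), so they will probably be near 100% too. That depends on how sites date AE onset, for which neither document sets a rule.
- *TEAE SOC/PT table by inhibitor subgroup (SAP 9.3.3).* The inhibitor has its own line, but the table counts patients per term. It does not separate serious events and cannot give the number of patients with any SAE other than the inhibitor.
- *SAE SOC/PT table (SAP 12).* It is by treatment regimen, so it does not identify inhibitor patients as a group.
- *Listings.* All SAEs are listed (SAP 9.3.7), and the listings mark AEs emergent after the inhibitor (SAP 9.3). The count can be made from them by hand.

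**The case against.** The strongest reply is that nothing turns on these rows. The analysis is descriptive, no hypothesis is tested, and the primary endpoint has its own analysis in SAP 9.4.3. The plan already splits safety data at the inhibitor date (SAP 5.4.7), and Protocol 16.5.2.2 has events during immune tolerance induction (ITI) summarized separately. The TEAE table shows the inhibitor term on its own line, and with perhaps 10 to 30 patients a count from a listing is quick. The assumed magnitudes only restate 100 - r, 100 - q and r - q. The proposed SAE row would not be a clean measure of other serious illness either, because major surgery is also a mandatory SAE.

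Most of this stands, and it sets the severity. It does not answer the central point: the plan chose to show these rows by inhibitor subgroup, and in that column they carry almost no information.

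Three stronger readings are tempting, and the documents do not support them.

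- *The rows must be exactly 100%.* Late confirmation and under-reporting can leave them slightly lower, as shown above.
- *The plan hides the safety of inhibitor patients.* The pre-inhibitor column, the ITI-regimen column, the discontinuation and death rows and the TEAE SOC/PT tables all remain informative.
- *A definite amount of post-inhibitor time is pooled with inhibitor-free patients in the prophylaxis column.* SAP 5.2.3 treats tapering as a move to the prophylactic regimen, but SAP 5.4.8 runs the ITI period until the patient completes or leaves the study. SAP 5.1.1.1 refers to both Section 5.2 and Section 5.4 for its periods, so the assignment is ambiguous. Patients who are eligible for ITI and decline it are withdrawn (Protocol 11), so those who never start it may add little time. No patient count or patient-time figure is justified.

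**Conclusion.** The concern holds as a minor point. With compliant reporting, the any-TEAE and any-SAE rows of the whole-period Inhibitor Subgroup column will be at or very near k/k whatever other events occur. Their comparison with inhibitor-free patients then reflects the subgroup definition. This follows from the definitions and needs no assumed rate; only the illustrated differences rest on assumed r and q. No planned summary table gives the number of inhibitor patients with an SAE other than the inhibitor over the whole period.

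A reader should not infer that the primary result is at risk. The inhibitor incidence and its confidence interval do not use these rows.

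**What to change.** In SAP 9.3.2, keep the all-event rows and add four: any TEAE, related TEAE, any SAE and related SAE, each excluding the inhibitor-development event. Flag that event in the AE data before database lock. State that the added rows are the ones to use when reading the table by inhibitor subgroup or across the inhibitor date. Add a footnote that the new SAE row still contains other mandatory SAEs, such as major surgery.

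Optionally, produce the SAE SOC/PT table by inhibitor subgroup as well.

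The cost is four rows, one flag and, if the option is taken, one table. No new data are needed and no planned output is lost.

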9.3.3. Summary of Treatment-Emergent Adverse Events

The overall incidence of TEAEs will be summarized by system organ class (SOC) and preferred term. SOC and preferred terms within each SOC will be presented alphabetically. For the purpose of summarization, a patient is counted once in a SOC or preferred term if the patient reported one or more events in that SOC or preferred term. This table will be presented by treatment regimen and for the inhibitor subgroups, as described in Sections 5.1.1.1 and 5.1.1.2 respectively.

This summary will also be presented by EPD entry compliance (see Section 6.6.2.3), <80% and $\geq 80\%$, where $\geq 80\%$ is considered compliant.

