5.1.1.1. General

There is only 1 treatment arm in the study. However unless otherwise stated, all analyses and background/demography tables will be presented for the following treatment groups, as defined in Section 3.1.2:

- Patients who were ever on an episodic regimen
- Patients who were ever on a prophylactic regimen
- Patients who were ever on an ITI regimen

For longitudinal data, the safety or efficacy periods included for these groups is the time spent on that regimen within that period. These periods are defined in Section 5.2 and 5.4.

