5.2.4. Duration of a Treatment Regimen

The duration of a given treatment regimen is the time period from the start of the treatment regimen to the end of that treatment regimen. The duration will stop and start for each treatment

	Statistical Analysis Plan	Final v1.0
---	----------------------------------	-------------------

regimen change. If a patient is treated in a given treatment regimen more than once, the total durations in the same treatment regimen will be added together. For example, if a patient is treated with the prophylactic regimen and then undergoes surgery and then goes back to the prophylactic regimen, then his total duration in the prophylactic regimen will be the sum of the two durations in the prophylactic regimen. Further details will be provided for individual analysis where needed.

The total duration of time allocated to each treatment regimen will be calculated in minutes and converted to days as the number of minutes divided by 1440.

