5.3.2. Categorical Variables

Categorical variables (e.g., ITI response) will be summarized using counts and percentages. All percentages will be rounded and presented to one decimal place, unless otherwise specified in the Statistical Programming Specifications for the study. The denominator for calculating percentages will depend on the variable to be summarized. For example, the denominator for calculating percentage of patients with any adverse event will be the Safety Analysis Set, which is number of patients dosed with rFVIIIFc.

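### Adverse events are tabulated only as crude percentages of patients, although time at risk can differ several-fold between regimen columns and between the periods before and after an inhibitor

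*SAP*

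**What the plan says.** The top-line table in SAP 9.3.2 "tabulates the number and percentage of patients who experienced a TEAE", and does the same for related and serious events. SAP 9.3.3 then provides that "The overall incidence of TEAEs will be summarized by system organ class (SOC) and preferred term", and in that table "a patient is counted once in a SOC or preferred term". SAP 5.3.2 gives the denominator as a count of people: "the denominator for calculating percentage of patients with any adverse event will be the Safety Analysis Set".

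The columns are set in 9.3.3: "This table will be presented by treatment regimen and for the inhibitor subgroups, as described in Sections 5.1.1.1 and 5.1.1.2 respectively". For the regimen columns, SAP 5.1.1.1 restricts follow-up: "For longitudinal data, the safety or efficacy periods included for these groups is the time spent on that regimen within that period". A patient who changes regimen contributes to more than one column (5.2). SAP 5.1.1.2 uses the entire period for the inhibitor yes/no tables, and splits it at the inhibitor date only for the sub-classification tables. SAP 9.3.7 summarises SAEs overall, and the table list in section 12 has a serious-event table by regimen but none by inhibitor group.

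The time at risk is largely derived already: "The total duration of time allocated to each treatment regimen will be calculated in minutes" (5.2.4), and 5.4.4 adapts the regimen periods for safety. It is not used in the adverse event tables. Neither SAP 9.3, the SAP table list nor Protocol 16.5.2.2 plans events per patient-year, events per exposure day or a time-to-event summary of adverse events. By contrast, bleeding and consumption are annualized in the same regimen and inhibitor columns (6.6.1.4, 7.4.3, 7.4.7), and 7.4.2 adds total patient-years to give context to the raw bleed counts.

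**The concern.** The percentage of patients with at least one event rises with follow-up even when the underlying rate is constant. If one column covers a few months and the next up to 33 months, the longer one is expected to show more patients with any given event without any difference in safety. A reader of the report could take a high ITI or post-inhibitor percentage as a signal, or a low episodic percentage as reassurance, when either may reflect duration alone. The same statistic can also rise between the interim and final analyses simply because patients have been followed longer.

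**Working it through.** The documents state no adverse event rate, so there is no planned figure to reproduce. The check asks what the planned statistic would show if the true rate were the same in every column.

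**Time at risk**
- ITI: at most 33 months (SAP 3.1.2.3), about 33 × 30.4375 = 1,004 days.
- Prophylaxis: at least 50 exposure days (SAP 3.1.2.2) at 3- to 5-day intervals (SAP 3.1.5.2). 50 × 3 = 150 days; 50 × 5 = 250 days; that is 4.9 to 8.2 months.
- Episodic: set by the Investigator (SAP 3.1.2.1). Assumed 3 months here, with 1 and 6 months as a range.
- After an inhibitor: at most 33 + 3 + 9 = 45 months (Protocol 7.3.2), about 1,370 days.
- Before an inhibitor: not stated. Assumed 10 exposure days at 3-day intervals (30 days) to 20 at 5-day intervals (100 days).

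**Ratios**
- ITI maximum to prophylaxis: 1,004/250 = 4.0 to 1,004/150 = 6.7.
- ITI maximum to episodic: 33/6 = 5.5 to 33/1 = 33.
- Post-inhibitor maximum to pre-inhibitor: 1,370/100 = about 14 to 1,370/30 = about 46.

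**Expected crude percentage**

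With constant rate r per patient-year and T years at risk, the expected percentage with at least one event is 100 × (1 − exp(−rT)). For example, at r = 0.2 over 33 months, rT = 0.2 × 2.75 = 0.55, and 1 − exp(−0.55) = 42.3%.

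| Assumed rate per patient-year | Episodic, 3 months | Prophylaxis, 150-250 days | ITI, 33 months |
|---|---|---|---|
| 0.2 | 4.9% | 7.9-12.8% | 42.3% |
| 1 | 22.1% | 33.7-49.6% | 93.6% |
| 6 | 77.7% | 91.5-98.4% | 100% |

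For the sub-classification tables at 0.2 per patient-year, the expected percentage is 1.6-5.3% before the inhibitor and 52.8% over the 45-month maximum after it.

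**When the gap closes**
- If ITI lasts 6 months (assumed), rT = 0.2 × 0.5 = 0.1 and the ITI percentage is 9.5%, inside the prophylaxis range.
- At high rates the percentage approaches its ceiling, as the last row of the table shows.

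**Does a rate remove the effect?** Take an illustrative 80 episodic patients for 3 months, 85 on prophylaxis for 200 days and 20 on ITI for 33 months, all at 0.2 per patient-year.
- Patient-years: 80 × 0.25 = 20; 85 × 200/365.25 = 46.5; 20 × 2.75 = 55.
- Expected events: 4.0, 9.3 and 11.0, which is 20 per 100 patient-years in each column.
- A Poisson simulation of this layout gave crude percentages of 4.8%, 10.4% and 42.3%, against rates of 19.8, 20.0 and 20.0 per 100 patient-years.

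**The case against.** The plan is descriptive throughout and proposes no comparison between regimens, which are phases of a single arm. Exposure days and duration of dosing are tabulated in the same columns (SAP 6.6.1.1 and 6.6.1.2), listings give onset days and mark events after an inhibitor (9.3), and safety tables generally carry a total column (5.1.1). The primary endpoint is inhibitor occurrence, where exposure is handled: a 10-exposure-day rule for the denominator, analyses at further milestones, and Kaplan-Meier estimates by exposure day (9.4.3). Actual time per regimen is unknown: ITI can succeed early (Protocol 10.2.7.4.2), end of study can cut it short, and tapering time is assigned to prophylaxis (SAP 5.2.3). A rate also assumes constancy over time and would not make the regimens comparable.

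Most of this stands, and it limits the point to how results are reported. Separate exposure tables do not answer it, because a count of patients with at least one event cannot be turned into events per patient-year.

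A reader might infer that the columns are bound to differ, or that the primary safety conclusion is compromised. The documents support neither. The size of the gap depends on durations they leave open, and no test or primary analysis uses these percentages. Nor are all inhibitor tables split before and after the event; only the sub-classification tables are.

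**Conclusion.** The point holds as a cheap improvement in reporting. The planned percentages mix event rate with duration, and the documents' own figures allow the ITI column 4.0 to 6.7 times the time that 50 prophylactic exposure days take. At equal rates that could produce about 42% against 8-13% for an event occurring at 0.2 per patient-year. This rests on an assumed constant rate, ITI at its maximum and prophylaxis stopping near 50 exposure days; shorter ITI or longer prophylaxis narrows the gap. The distortion is greatest for individual preferred terms and SAEs, and small for the proportion with any event if nearly all patients have one.

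**What to change.** Add patient-years at risk and events per patient-year (or per 100 patient-years) alongside the existing percentages:
- in each regimen column of the tables in SAP 9.3.2 and 9.3.3 and the by-regimen SAE table under 9.3.7;
- in the before and after columns of the inhibitor sub-classification tables in 9.3.2 and 9.3.3;
- in the inhibitor yes/no tables in 9.3.2 and 9.3.3, using total follow-up.

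Use the safety period in 5.4.4 as the denominator, with two rules so that numerator and denominator match:
- SAP 9.3 counts events in major surgical/rehabilitation periods only in the top-line table. Remove that time from the denominator in every other table.
- For patients who start on episodic treatment, the regimen begins 120 hours after the baseline PK dose (5.2.1), while the overall safety period begins at first dose (5.4.4). State which column takes that initial time and its events.

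The cost is modest programming, since the regimen start and stop times are already derived, plus a separate time-at-risk rule for the top-line table. A footnote should say that the rates remain descriptive, because regimens also differ in age, order and inhibitor status.
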